# 4.1.7 DISCONTINUATION/WITHDRAWAL PROCEDURES

A subject may voluntarily withdraw from study participation at any time, for any reason. If the subject withdraws consent and discontinues from the study, the Investigator will attempt to determine the reason for discontinuation and record the reason in the subject's study records and in the study database. If a subject is withdrawn because of an AE, that AE should be indicated as the reason for withdrawal. In the event of early discontinuation, (i.e., prior to Week 12/Day 84 visit) and whenever possible, the subject should be asked to return to the study center to complete the Week 12/ET evaluations. Subjects who withdraw from the study will not be replaced.

If at any time during the study the Investigator determines that it is not in the best interest of the subject to continue, the subject will be discontinued from participation. The Investigator can discontinue a subject at any time if medically necessary. The Investigator may discontinue a subject's participation if the subject has failed to follow study procedures or to keep follow-up appointments. Appropriate documentation in the subject's study record and the study database regarding the reason for discontinuation must be completed.

All subjects who fail to return to the study center for the Week 12/ET visit will be contacted by telephone to determine the reason(s) why the subject failed to return for the necessary visit or elected to discontinue from the study. If a subject is unreachable by telephone after a minimum of

two documented attempts (one attempt on two different days), a certified letter will be sent requesting that the subject contact the Investigator.

Reasons for an Investigator's withdrawal of a subject may include, but are not limited to, the following:

- Safety (e.g., severe adverse reactions, pregnancy);
- Lack of efficacy as determined by the Investigator;
- When the requirements of the protocol are not adhered to (e.g., significant issues with dosing compliance);
- When a concomitant medication or treatment likely to interfere with the results of the study is reported, or required, by the subject (the Investigator will decide, in consultation with PPD, whether the subject is to be withdrawn);

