- When a subject is lost to follow-up. The Investigator will try twice to reach the subject by telephone (one call, two separate days) and will send a certified follow-up letter before considering that the subject is lost-to-follow-up. These actions will be reported on the subject's study record and a copy of the follow-up letter maintained in the Investigator's file.

Refer to Section 6.7 for a discussion of criteria for discontinuation of individual subjects from the study.

All premature discontinuations and their causes must be carefully documented by the Investigator on the subject's study record and in the study database. In no case will a subject who has been assigned a study number and randomized into the study be replaced by another.

All Week 12/ET evaluations should be performed at the time of premature discontinuation. All data gathered on the subject prior to termination will be made available to PPD and Novan.

Study completion or reason(s) for discontinuation as listed in the study record will be entered into the study database as follows:

- Completed
- Adverse Event
- Lack of Efficacy
- Withdrawal by Subject
- Physician Decision
- Protocol Violation
- Lost to Follow-Up

- Pregnancy
- Worsening of condition
- Other

Novan has the right to terminate or stop the study at any time. Should this be necessary, both PPD and the Investigator will ensure that proper study discontinuation procedures are completed.

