### 5. PROHIBITED THERAPIES AND MEDICATIONS

Concomitant medications are any prescription or OTC preparations. Use of concomitant medications will be recorded on the concomitant medications study record and study database beginning at the Baseline Visit until the final evaluation (Week 12/ET).

Subjects must not have used anti-wart treatments including topical treatments or procedures as described in Section 3.7.3 for at least 28 days prior to Baseline. These medications/treatments are also prohibited during the trial.

Subjects may not be concurrently on nitroglycerin, drugs associated with methemoglobinemia, drugs to treat EGW/PAW, or drugs/supplements that are nitric oxide releasers (Appendix 1). Subjects who have used an investigational drug or device within 30 days of Baseline should not be enrolled. Subjects must not participate in a different interventional research study during the study period. Any subject who has participated in a previous study with SB204 Gel/NVN1000 Gel is ineligible for enrollment.

Any medication/therapy used by the subject following first application of study product will be considered a concomitant medication/therapy (e.g., aspirin, acetaminophen, birth control pills, vitamins, etc.). Every attempt should be made to keep concomitant medication/therapy dosing constant during the study. Any change to concomitant medications/therapies should be noted on the subject's study record and in the study database. When applicable, an AE should be completed for any subject starting a concomitant medication/therapy after randomization into the study.

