#### 7.5.1 PRIMARY EFFICACY ANALYSIS

The number and proportion of subjects with complete clearance of baseline warts will be summarized by treatment group and each active dose group will be compared to vehicle using pairwise Pearson's chi-square tests. The odds ratios and corresponding 95% CI will be presented. The pairwise comparisons of each active treatment group to the Vehicle Gel treatment group will be computed without concern for controlling for multiplicity.

Percentages will be calculated out of the number of subjects in the analysis population. Subjects who have a clearance of baseline warts at or before the Week 12 visit will be counted as cleared for the analysis. Subjects who do not have a documented clearance by the end of study, including subjects with missing data at the Week 12 or other assessments, will be considered not cleared for the analysis.

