#### 4. General Statistical Considerations

All statistical processing will be performed using SAS® version 9.2 or higher unless otherwise stated. Statistical significance will be based on two-tailed tests of the null hypothesis resulting in p-values of  $\leq 0.05$  unless stated otherwise. Inferential testing will compare each active treatment group to the vehicle treatment group. Comparisons will not be performed between active treatments. All p-values will be reported without concern for controlling for multiplicity. Efficacy analyses will be performed for the intent-to-treat (ITT) and per-protocol (PP) populations. Safety analyses will be performed using the safety population as defined in section 4.3.2

Continuous data will be summarized with sample size (N), mean, median, standard

deviation, minimum and maximum. Categorical data will be summarized with number of subjects N, frequency counts, and percentages.

For analysis, baseline warts are defined as warts that are present at the baseline visit. Total warts include all warts present, even if they were not present at the baseline visit. Complete clearance is defined as zero warts present. Partial clearance is defined as a reduction in number of warts from baseline.

The last evaluation for each endpoint prior to the first dose of study drug will be used as baseline for all analyses.

For safety analyses including tolerability, summaries will be performed by treatment arm as well as "Pooled Active", which is a total of all NVN1000 treatment arms.

For disposition, demographics, efficacy, compliance and tolerability analyses, Vehicle Gel subjects will be summarized separately by dosing frequency (QD and BID). For other safety analyses, vehicle subjects will be combined. Subjects will be listed by actual treatment, with vehicle subjects listed separately by dosing frequency.

For subjects who are taken off treatment due to complete clearance of warts and then later restart treatment due to recurrent warts, the date of last dose for analysis purposes will be the date of last dose for the second treatment interval.

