## 4.3.3. Per-Protocol Population

The PP population will include subjects with no noteworthy study protocol deviations (i.e., any subject or investigator activity that could have possibly interfered with the therapeutic administration of the treatment or the precise evaluation of treatment efficacy) prior to initial clearance of baseline warts, or Week 12/early termination if the subject does not achieve complete clearance at any time during the study. The PP population will include subjects in the safety population who do not meet any of the following criteria:

- Violated inclusion/exclusion criteria which have a potential impact on efficacy
- Have taken any concomitant medications likely to impact efficacy
- Have missed more than one interim study visit that they would have been eligible to attend as their EGW/PAW had not completely resolved
- Have not been compliant with the dosing regimen (i.e., subjects must apply 80-120% of the expected applications of study medication during participation in the study)

All significant protocol deviations will be documented in the Significant Protocol Deviations Rules document. Each significant deviation will be assigned a rule number and indication (yes/no) if the deviation will result in subject exclusion from the PP population. Prior to breaking the blind, other additional criteria may be added to the list to accommodate for unforeseen events that occurred during the conduct of the trial that result in noteworthy study protocol deviations. A by subject listing will be presented including the reason subjects are not included in any analysis population.

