### 4.4.2. Visit Windows

By-visit analyses will be performed using the reported CRF visit. The one exception is the Week 12/ET visit. For safety endpoints that are not measured at every visit (e.g. lab values and vital signs), the Week 12/ET will be mapped to Week 12 but presented in tables/listings as Week 12/ET. For all other endpoints, for subjects who complete the study, the Week 12/ET visit will be mapped to "Week 12" and used in by visit analyses. For subjects who are early terminations, the Week 12/ET visit will be mapped to "ET" (early term and will not be included in the by visit analyses. The ET visit may be used for LOCF of missing data. The ET visit will be carried forward only to visits for which the ET visit occurred prior to on the last study day of the analysis visit window using the following windows:

Analysis Visit	Visit Window (Based on Study Day)
Week 2	Day 2 to Day 22
Week 4	Day 23 to Day 45
Week 8	Day 46 to Day 71
Week 12	Day 72 +

Table 1: Analysis	Visit	Windows
-------------------	-------	---------

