#### 8.1. Primary Efficacy Endpoint

## 8.1.1. Proportion of Subjects with Complete Clearance of Baseline EGW/PAW at or Before Week 12

The primary efficacy endpoint is the proportion of subjects with complete clearance of baseline EGW/PAW at or before Week 12.

The number and proportion of subjects with complete clearance of baseline warts will be summarized by treatment group and each active dose group will be compared to vehicle using pairwise Pearson's chi-square tests. The Mantel-Haenszel odds ratios and corresponding 95% confidence interval (CI) will be presented. The Vehicle Gel arm will be separated into once-daily (QD) and twice-daily (BID) groups and compared pairwise to the corresponding active treatments. The three once-daily active treatment groups (8%, 16%, and 24%) will be compared to the Vehicle Gel QD group and the NVN1000 8% BID group will be compared to the Vehicle Gel BID group. The pairwise comparisons will be computed without concern for controlling for multiplicity. The primary analysis will be performed for the ITT population.

Percentages will be calculated based on the number of subjects in the ITT analysis population. Subjects who have clearance of baseline warts at or before the Week 12 visit will be counted as cleared for the analysis. Subjects who do not have a documented clearance by the end of study, including subjects with missing data at the Week 12 or other assessments, will be considered not cleared for the analysis.

The primary analysis will be repeated for the PP population. Subgroup analysis for gender and wart location (EGW/PAW) will also be performed for the ITT population. The subgroup summaries will be descriptive only with no statistical hypothesis testing performed.

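### The primary ITT rule scores a subject as cleared even when a prohibited anti-wart medication or procedure removed the baseline warts

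*SAP*

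**What the plan says.** The primary responder rule is in SAP 8.1.1: "Subjects who have clearance of baseline warts at or before the Week 12 visit will be counted as cleared for the analysis". Protocol 7.5.1 has practically the same sentence: "Subjects who have a clearance of baseline warts at or before the Week 12 visit will be counted as cleared for the analysis". SAP 4 supplies the definition: "Complete clearance is defined as zero warts present". The only stated route to non-response is the absence of a documented clearance, including through missing data. SAP 8 restricts the endpoint to the first instance of clearing but does not ask what produced it. The primary population is ITT: everyone randomized and dispensed drug (SAP 4.3.1).

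On other wart treatment, Protocol 5 points to the medications and procedures listed in Protocol 3.7.3, which include cryotherapy and laser surgery, and adds: "These medications/treatments are also prohibited during the trial". Protocol 4.1.7 lists among the possible reasons for withdrawal: "When a concomitant medication or treatment likely to interfere with the results of the study is reported, or required, by the subject". The investigator takes that decision together with the contract research organisation. For those withdrawn: "All Week 12/ET evaluations should be performed at the time of premature discontinuation". Protocol 4.1.6 includes wart counts in that visit.

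Two other passages bear on the handling. SAP 4.3.3 excludes from the per-protocol population subjects who "Have taken any concomitant medications likely to impact efficacy", alongside a general exclusion for noteworthy deviations before initial clearance. SAP 4.4.2 says of early-termination data: "The ET visit may be used for LOCF of missing data".

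**The concern.** The primary endpoint is there to show how often baseline warts clear under NVN1000 or vehicle. A wart that was frozen or cut off says nothing about either gel, yet the rule as written scores that subject as a success. The protocol foresees that interfering treatment will occur, but the analysis plan does not say how it is scored in ITT.

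At stake is how the clearance estimate is interpreted. Responder status would be wrong for each affected subject, and the groups are small enough for one or two such subjects to show. The same endpoint in the same population is among the interim outputs (SAP 10, Table 2) that are meant to help plan future trials.

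**Working it through.** **Step 1. Follow one subject through the plan.** No figure in the documents can be reproduced: they give no clearance rate, no rate of prohibited treatment and no power. The first check is therefore a reading. Take a subject with baseline warts at Week 4 who has cryotherapy at Week 6.

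- If the subject stays in the study and has a zero baseline-wart count at Week 8, SAP 8.1.1 scores cleared.
- If the subject is withdrawn, the Week 12/ET evaluations are done then. A zero count at that visit is a documented clearance before Week 12, so SAP 8.1.1 again scores cleared.
- ITT membership (SAP 4.3.1) does not change in either case.
- In the by-visit secondary endpoints, SAP 4.4.2 allows the early-termination zero to be carried forward, within its windows.
- In SAP 8.2.8 the same zero is an event for time to clearance.
- In the per-protocol repeat the subject leaves both numerator and denominator. SAP 7.1 defines concomitant medications as medicinal products, so the listed criterion does not name cryotherapy. Only the general deviation wording, or the separate deviation rules document, reaches it.

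**Step 2. Group sizes.** Inputs: about 120 subjects at 3:1 in four cohorts (Protocol synopsis; SAP 3.1 and 4.1), with vehicle split by dosing frequency (SAP 8.1.1). Assumption: equal cohorts of 30.

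- Active: 120 × 3/4 = 90; 90/4 = 22.5 per dose group.
- Vehicle: 120 × 1/4 = 30; 30/4 = 7.5 per cohort.
- Once-daily vehicle (Cohorts 2 to 4): 3 × 7.5 = 22.5. Twice-daily vehicle (Cohort 1): 7.5.

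**Step 3. Shift per affected subject** (1/n):

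| Group | n | Shift in clearance rate |
|---|---|---|
| One active dose, or once-daily vehicle | 22 to 23 | 4.5 to 4.3 points |
| Twice-daily vehicle | 8 to 7 | 12.5 to 14.3 points |

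**Step 4. Direction.** Let p be the true clearance rate and u the share of non-responders cleared by a prohibited treatment. The scored rate is p + (1 − p)u, so the difference between groups changes by (1 − pA)uA − (1 − pV)uV. With assumed rates pA = 35% and pV = 10% (true difference 25 points):

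| uA | uV | Scored active | Scored vehicle | Difference |
|---|---|---|---|---|
| 5% | 10% | 0.35 + 0.65 × 0.05 = 38.2% | 0.10 + 0.90 × 0.10 = 19.0% | 19.2 points |
| 10% | 10% | 0.35 + 0.65 × 0.10 = 41.5% | 19.0% | 22.5 points |
| 10% | 0% | 41.5% | 10.0% | 31.5 points |

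The difference shrinks in the first two rows and grows in the third. At these rates it is inflated when uA exceeds 0.90/0.65 = 1.38 times uV.

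**The case against.** The strongest reply is that this is an omission and a matter of preference. No sentence says that subjects treated elsewhere are successes. Counting observed outcomes in everyone randomized and dispensed, with a per-protocol repeat, is a recognised approach. The missing-data rule concerns absent counts, whereas this concerns an observed one. The treatments are prohibited, withdrawal is available, and cryotherapy on a baseline wart plainly meets the general deviation wording in SAP 4.3.3.

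Much of that is fair. Scoring prohibited treatment as non-response is a choice, and the per-protocol repeat is a real though partial safeguard. It does not remove the point. The primary rule, followed exactly, still yields a success, and the repeat excludes the subject instead of counting a failure.

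Two stronger readings are tempting and are not supported.

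- A reader might infer that the rule hides a drug effect, because vehicle subjects have more reason to seek other treatment. The documents give no use by arm. Subjects stopping for intolerance may seek it too: Protocol 1.5 reports two such discontinuations in Cohort 1 with treatment unknown.
- A reader might infer that one subject decides significance. With assumed counts of 8/22 against 0/8, Pearson p is 0.046, and 1/8 gives 0.207. But 8/23 against 0/7 already gives 0.068, and the smallest expected count in the 8/22 against 0/8 table is 8 × 8/30 = 2.1, too low to trust the test. The study is not powered for efficacy, so crossing 0.05 decides little.

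**Conclusion.** The point holds for the primary ITT analysis as written: clearance produced by a prohibited anti-wart medication or procedure counts as a treatment success, and nothing elsewhere in the protocol or SAP overrides this. The direction of the resulting bias is unknown.

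The dependable measure of size is the shift per affected subject in Step 3, which rests on equal cohorts of 30. SAP 4.1 lets cohort sizes vary with safety-board recommendations and enrolment, so the actual shifts may differ. How many subjects would be affected is not stated and may be few. This is a matter of interpreting the estimate in an unpowered phase 2 study, and worth correcting because the correction is simple.

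**What to change.** Settle the following before treatment codes are opened for any efficacy analysis, including the interim.

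- **SAP 8.1.1 and 8.2.1** (recording the change from Protocol 7.5.1): wart counts on or after the date of the first prohibited anti-wart medication or procedure are not used as evidence of clearance. A subject with no documented clearance before that date is counted as not cleared.
- **SAP 8.2.2**: apply the same rule to complete or partial clearance, keeping any response documented before that date, so that a genuine earlier partial response is not erased.
- **SAP 8.2.3 to 8.2.7**: do not use counts on or after that date; treat them as missing under the existing LOCF rule.
- **SAP 8.2.8**: a zero first reached on or after that date is not an event. Treat the subject as not cleared, consistent with the primary analysis.
- **SAP 4.3.3**: extend the medication criterion to medications or procedures.
- **Data source**: flag such treatment and its date from the concomitant medication/therapy records described in Protocol 5 and from the deviation log. The schedule of events lists only concomitant medications, so confirm that procedures are captured.
- **Sensitivity analysis**: retain the current rule.

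The cost is SAP wording and one extra derivation, with no new visit or assessment and no change to clinical management. Clearance rates may come out slightly lower.

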#### 8.2. Secondary Efficacy Endpoints

The secondary efficacy analysis will be performed for both ITT and PP.

# 8.2.1. Proportion of Subjects with Complete Clearance of Total EGW/PAW at or Before Week 12.

The number and proportion of subjects with complete clearance of total EGW/PAW will be summarized by treatment group and each active dose group will be compared to its corresponding vehicle group using pairwise Pearson's chi-square tests. The Mantel-Haenszel odds ratios and corresponding 95% CI will be presented.

Subjects who have clearance of baseline warts at or before the Week 12 visit will be counted as cleared for the analysis. Subjects who do not have a documented clearance by the end of study, including subjects with missing data at the Week 12 or other assessments, will be considered not cleared for the analysis.

Subgroup analysis for gender and wart location (EGW/PAW) will also be performed for the ITT populations. The subgroup summaries will be descriptive only with no statistical hypothesis testing performed.

# 8.2.2. Proportion of Subjects with Complete or Partial Clearance of Baseline EGW/PAW at or Before Week 12

The number and proportion of subjects with complete or partial clearance, defined as a reduction in the number of baseline EGW/PAW, will be summarized by treatment group and each active dose group will be compared to its corresponding vehicle group using pairwise Pearson's chi-square tests. The Mantel-Haenszel odds ratios and corresponding 95% CI will be presented.

Subjects who have clearance, complete or partial, of baseline warts at or before the Week 12 visit will be counted as cleared or partially cleared for the analysis. Subjects who do not have a documented clearance or partial clearance by the end of study, including subjects with missing data at the Week 12 or other assessments, will be considered not cleared or partially cleared for the analysis.

## 8.2.3. Proportion of Subjects with Complete Clearance of baseline EGW/PAW at Weeks 2, 4, 8, and 12

The number and proportion of subjects with complete clearance of baseline EGW/PAW at each post-baseline visit will be summarized by treatment group and each active dose group will be compared to its corresponding vehicle group using pairwise Pearson's chi-square tests. The Mantel-Haenszel odds ratios and corresponding 95% CI will be presented.

Imputation of missing data will be performed using a last-observation carried forward (LOCF) method where a missing assessment is replaced by the previous visit's assessment.

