### 3.1 STUDY ENDPOINTS

# 3.1.1 EFFICACY ENDPOINTS

For the primary efficacy analyses, efficacy will be based on warts which are present at baseline.

Selected summaries will be presented for total warts counts, including warts present at baseline and warts that arise during the treatment period. Total wart counts will be based on any wart(s) observed at the given visit, including warts that were not present at baseline.

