### 7.5.2 SECONDARY EFFICACY ANALYSES

The number and proportion of subjects with complete clearance of total warts, and the number and proportion of subjects with complete or partial clearance of baseline warts at or by Week 12 will be assessed in a similar manner to the primary efficacy endpoint. The response over time will be similarly assessed for the proportion of subjects and total number of warts with complete clearance of baseline and total EGW/PAW. The time to complete clearance of baseline warts will be summarized. Each active dose group will be compared to vehicle using pairwise Pearson's chi-square tests and the odds ratios and corresponding 95% CIs will be presented.

For those subjects in whom complete clearance of baseline warts is achieved prior to Week 12, recurrence of baseline warts will be assessed.

Descriptive summaries will be provided for percent change in baseline wart counts and total wart counts. Each active dose group will be compared to vehicle using pairwise t-tests and the corresponding 95% CIs for the differences in treatment means will be presented. Subgroup analysis for gender and wart location (EGW/PAW) will also be performed.

The secondary endpoints will include:

- Proportion of subjects with complete clearance of total EGW/PAW at or before Week 12;
- Proportion of subjects with a complete or partial clearance of baseline EGW/PAW at or before Week 12. A partial clearance is defined as a reduction in the number of baseline warts;
- Proportion of subjects with complete clearance of baseline EGW/PAW at Weeks 2, 4, 8 and 12;

- Proportion of subjects with complete clearance of total EGW/PAW at Weeks 2, 4, 8 and 12;
- Proportion of subjects with a complete or partial clearance of baseline EGW/PAW at Weeks 2, 4, 8 and 12;
- Percent reduction in baseline EGW/PAW wart counts at Weeks 2, 4, 8 and 12;
- Count of baseline warts and count of total warts at Weeks 2, 4, 8 and 12;
- Time to complete clearance of baseline warts;
- Recurrence of baseline warts cleared prior to Week 12.

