#### 3.2.2. Secondary Efficacy Endpoints

The secondary endpoints will include:

• Proportion of subjects with complete clearance of total EGW/PAW at or before Week 12

- Proportion of subjects with a complete or partial clearance of baseline EGW/PAW at or before Week 12. A partial clearance is defined as a reduction in the number of baseline warts.
- Proportion of subjects with complete clearance of baseline EGW/PAW at Weeks 2, 4, 8, and 12
- Proportion of subjects with complete clearance of total EGW/PAW at Weeks 2, 4, 8, and 12
- Proportion of subjects with a complete or partial clearance of baseline EGW/PAW at Weeks 2, 4, 8, and 12
- Count of baseline warts and count of total warts at Weeks 2, 4, 8, and 12
- Percent and raw reduction in baseline EGW/PAW wart counts at Weeks 2, 4, 8, and 12
- Time to complete clearance of baseline warts
- Recurrence of baseline warts cleared prior to Week 12

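### SAP 8.2.1 scores total-wart clearance with the baseline-wart rule, so as written it repeats the primary endpoint and can overcount subjects who never became wart-free

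*SAP*

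**What the plan says.** Both documents list total-wart clearance as a secondary endpoint separate from the primary. SAP 3.2.2 gives it first: "Proportion of subjects with complete clearance of total EGW/PAW at or before Week 12". The opening paragraph of SAP 8.2.1 agrees: "The number and proportion of subjects with complete clearance of total EGW/PAW will be summarized by treatment group".

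SAP section 4 supplies the definitions:

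- Baseline: "baseline warts are defined as warts that are present at the baseline visit".
- Total: "Total warts include all warts present, even if they were not present at the baseline visit".
- Complete clearance: "Complete clearance is defined as zero warts present".

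Protocol 3.1.1 describes the total count in the same way: "Total wart counts will be based on any wart(s) observed at the given visit, including warts that were not present at baseline". Protocol 7.5.2 says that the total-wart endpoint "will be assessed in a similar manner to the primary efficacy endpoint".

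The second paragraph of SAP 8.2.1 then sets the scoring rule: "Subjects who have clearance of baseline warts at or before the Week 12 visit will be counted as cleared for the analysis". The same sentence stands in SAP 8.1.1 as the rule for the primary endpoint.

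**The concern.** The section names one endpoint and scores another. The total-wart endpoint exists to show whether subjects became free of all warts, including those that appeared on treatment. A rule that looks only at baseline warts cannot show that.

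It also sits badly with how the trial treats subjects. Under the Protocol Synopsis, new warts are treated as they arise. Under Protocol 4.2.1 and SAP 3.1, application stops altogether only when all warts have cleared. A subject still treating new warts could therefore be reported as having complete clearance of total warts.

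If the sentence is followed, the report will carry a second table, labelled as total clearance, that adds nothing to the primary table and may overstate the result. If the heading and section 4 are followed instead, the table will be different. Two competent programmers could thus produce different results from the same SAP.

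**Working it through.** The plan states no clearance rate, effect size or power for this endpoint, so there is no figure of its own to reproduce. The check is on the definitions.

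**1. The two sections side by side**

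| Element | SAP 8.1.1 (primary) | SAP 8.2.1 (total warts) |
|---|---|---|
| Endpoint named | Clearance of baseline warts | Clearance of total warts |
| Responder rule | Baseline warts cleared by Week 12 | Baseline warts cleared by Week 12 (same sentence) |
| No documented clearance, or missing data | Not cleared | Not cleared |
| Test and estimate | Pearson chi-square, Mantel-Haenszel odds ratio | Same |
| Comparator | Vehicle group of matching frequency | Same |
| Populations | ITT, repeated in PP | ITT and PP (SAP 8.2) |

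Only the name differs. Numerator, denominator, p-value and odds ratio are therefore the same in every comparison.

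**2. Which subjects are misclassified**

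At each of the four post-baseline visits (Weeks 2, 4, 8, 12), baseline warts are present or absent and new warts are present or absent. That gives 4 states per visit and 4⁴ = 256 patterns.

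- Responder under 8.1.1, and under 8.2.1 as written: baseline count 0 at one or more visits. Non-responders have baseline warts at all four visits: 2⁴ = 16 patterns. Responders: 256 − 16 = 240.
- Responder under section 4: baseline and new counts both 0 at the same visit, at least once. Non-responders never occupy that state: 3⁴ = 81 patterns. Responders: 256 − 81 = 175.
- 8.2.1 as written against the primary: 0 differences in 256.
- 8.2.1 as written against section 4: 240 − 175 = 65 overcounts and 0 undercounts.

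These are counts of patterns, not probabilities. The 65 are the patterns in which the baseline count reaches 0 but a new wart is present at every such visit. A subject who has new warts at some time but a total count of 0 at any visit is scored correctly.

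**3. Effect on the responder rate (assumed inputs)**

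Overstatement = P(baseline warts clear) × P(total count never 0 | baseline warts clear).

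- Lower: 0.30 × 0.10 = 0.03
- Upper: 0.30 × 0.30 = 0.09

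That is 3 to 9 percentage points. Neither the 30% nor the 10–30% comes from the documents.

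**4. Effect on the comparison (assumed inputs)**

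Take 23 subjects on active and 22 on once-daily vehicle, with baseline warts cleared in 8 and 3. The odds ratio is (8 × 19)/(15 × 3) = 3.38. The Pearson chi-square without continuity correction is 45 × (8 × 19 − 15 × 3)²/(23 × 22 × 11 × 34) = 2.72, p = 0.099. The rule as written reports these figures again for total warts. Scored on total counts, rounded to whole subjects:

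| Clearers who never reach a total count of 0 | Active | Vehicle | Odds ratio | p |
|---|---|---|---|---|
| None (equals rule as written) | 8/23 | 3/22 | 3.38 | 0.099 |
| 10% in both arms | 7/23 | 3/22 | 2.77 | 0.18 |
| 25% in both arms | 6/23 | 2/22 | 3.53 | 0.14 |
| 50% in both arms | 4/23 | 2/22 | 2.11 | 0.41 |
| 25% in active only | 6/23 | 3/22 | 2.24 | 0.30 |
| 1 of 3 in vehicle only | 8/23 | 2/22 | 5.33 | 0.038 |

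The error in the rate has one direction. The error in the treatment comparison does not.

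**The case against.** The best defence is that this is one carried-over sentence in a section that otherwise means what it should. The 8.2.1 heading and first paragraph, the endpoint lists, the protocol and section 4 all say total warts, and a programmer who followed them would get the intended endpoint. That is true, and the duplication follows only if the scoring sentence is obeyed. But it is the only sentence in 8.2.1 that says who counts as cleared, and nothing elsewhere overrides it. The scoring sentence in 8.2.2 was adapted to its endpoint, which suggests an oversight in 8.2.1 rather than a choice. The protocol's call for similar handling to the primary concerns the method; it does not turn total warts into baseline warts.

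A second line is that little depends on this endpoint. The study is not powered for efficacy, there is no multiplicity control or testing hierarchy, the 8.2.1 table is not among the interim outputs, and no stopping rule or dose step uses it. Total-wart information also survives in 8.2.4, 8.2.7 and the listings. All of this stands and limits the consequence to the interpretation of one secondary endpoint. It does not make the rule right.

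Third, a mismatch between 8.2.1 and 8.2.4 would not by itself show an error: the first is ever-cleared with missing counted as not cleared, the second is by visit with LOCF. That is fair. The mismatch that does reveal the defect is narrower. With complete data, a subject whose total count is never 0 is not clear at any visit in 8.2.4 but is cleared in 8.2.1.

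Finally, the true overcount could be zero. It would be if every subject who cleared baseline warts also had a total count of 0 at some visit. The documents do not allow that to be judged.

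**Conclusion.** The scoring rule in SAP 8.2.1 is wrong as written. It contradicts its own section and section 4, and if applied it reproduces the primary result in every arm and both populations under a label that promises something else. Any misclassification overcounts total clearance and is confined to subjects with a new wart at every visit where their baseline count is zero. These conclusions rest on the text alone.

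The size is unknown. The 3–9 points and the tabulated p-values are illustrations on assumed inputs. The primary endpoint, significance level and sample size are not affected.

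**What to change.** In SAP 8.2.1, change the responder sentence so that a subject is cleared when the total wart count (baseline plus new warts) is 0 at a single visit, at or before the Week 12 visit. Keep the rule that missing or undocumented clearance counts as not cleared, and say that it refers to clearance of total warts. SAP 7.2.1 already uses a total wart count of 0 in its compliance rule, so the term is available.

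After the change, responders in 8.2.1 are a subset of the primary responders. That gives a simple programming check: in every arm, total clearance must not exceed baseline clearance.

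The cost is one sentence in a SAP revision and one derived flag. Protocol 4.1.3 to 4.1.6 and 4.2.1 already have baseline and total counts recorded at each post-baseline visit, so no new data, subjects or protocol amendment are needed. Make the change before the analysis team sees unblinded efficacy data, including at the interim analysis of Cohorts 1 and 2, because a later correction could look driven by the results.
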